**C: From special parasternal long-axis window (RV inflow)**

19. 2D Colour Doppler of tricuspid regurgitation (TR)
20. If TR is present, CWD of TR jet (frozen image)

**D: From the apical 4-Chamber window**

21. 2D greyscale standard view
22. 2D Colour Doppler of MR
23. If MR is present, ZOOM & narrow sector, shift Nyquist 35-40 for PISA measurements
24. If MR is present, CWD of MR jet (frozen image)
25. 2D Colour Doppler of TR
26. If TR is present, CWD of TR jet (frozen image)

27. PWD of transmitral flow at mitral valve tips – at a sweep speed of 50-100 mm/s (frozen image)
28. Tissue Doppler of the septal mitral annulus – (frozen image)
29. Tissue Doppler of the lateral mitral annulus – (frozen image)
30. Tissue Doppler of RV free wall (frozen image)
31. M-mode tricuspid annular plane systolic excursion (TAPSE) – (frozen image)
32. 2D greyscale focussed on LV with decreased depth – three recordings: 3 beats, 3 beats, 10 beats)

**E: Apical 5-chamber window**

33. 2D greyscale standard view
34. 2D Colour Doppler of AR
35. If AR is present, ZOOM & narrow sector, shift Nyquist 35-40 for PISA measurements
36. If AR is present, CWD of AR jet (frozen image)
37. CWD of aortic forward flow (frozen image)
38. PWD LVOT in native aortic valve: within 0.5 - 1cm below native aortic valve
39. PWD LVOT in Core Valve, two recordings: immediately below and inside the inflow region of the stent

**F: Apical 2-Chamber window**

40. 2D greyscale standard view
41. 2D greyscale focussed on LV with decreased depth – three recordings: 3 beats, 3 beats, 10 beats)

**G: Apical 3-chamber window**

42. 2D greyscale standard view
43. 2D Colour Doppler of MR
44. If MR is present, use ZOOM & narrow sector – shift Nyquist 35-40 for PISA measurements
45. If MR is present, CWD of MR jet (frozen image)
46. 2D Colour Doppler of AR
47. If AR is present, CWD of AR jet (frozen image)
48. If AR is present, use ZOOM & narrow sector– shift Nyquist 35-40 for PISA measurements
49. CWD of aortic forward flow (frozen image)
50. PWD LVOT in native aortic valve: within 0.5 - 1cm below native aortic valve
51. PWD LVOT in Core Valve, two recordings: immediately below and inside the inflow region of the stent
52. 2D greyscale focussed on LV with decreased depth – three recordings: 3 beats, 3 beats, 10 beats)

**H: special recordings**

53. Suprasternal PWD of descending aorta diastolic flow (frozen image)
54. Subcostal PWD of abdominal aortic diastolic flow (frozen image)
55. CWD right parasternal aortic forward flow (frozen image)
56. 2D greyscale inferior vena cava – **sniff test for changes in IVC diameter**
57. Optional – biplane imaging at LVOT long-axis for measurement of LVOT area in SAX
58. Optional – 3D full volume acquisition of parasternal long-axis view focus LVOT and aortic root
59. Optional – 3D apical full volume acquisition (single beat or 7 beats)
60. Optional – 3D Colour Doppler from apical view – region of interest aortic valve for AR

**6. Detailed instructions for acquisition of SURTAVI echocardiography recordings**

6.1 Quality control of the investigational site (initial site validation)

- The 1st subject with an echo examination submitted will be reviewed to assess the quality of the recording and the transmission and most importantly the ADHERENCE to the PROTOCOL.
- A "Core Laboratory Pre-Analysis" Report will be provided to the site

6.2 Guidelines for study object confidentiality

- **NO patients' information should be present** on the echocardiogram.
- Site-Patient identification: study subjects are to be identified by a specific study identification number as supplied by the sponsor.
- The following items should be entered in the patient identification section of ultrasound system and should be clearly shown on all digital cine loops or still frames.
  - Site-subject ID (XXXXX-YYYY)
  - date of exam and
  - study interval
- To ensure adherence to the USA HIPAA (Health Insurance Portability and Accountability Act of 1996) guidelines for study subject confidentiality, no study subject names or other Protected Health Information (date of birth, hospital record number, etc.) should be displayed.

6.3 Submission

- Upload all study echocardiograms to InteleGRID (secure electronic system used for transferring images)

6.4 Further inquiries:

- For any questions, contact your monitor or Medtronic Clinical Research Specialist

## 7. Technical guidelines: how to optimize the echocardiography images

### 7.1 General recording recommendations

- Ensure ultrasound machines are maintained as instructed by the manufacture
- Ensure calibration of distance, velocity and time on each image
- Keep persistence and smoothing off

### 7.2 ECG gating

- All cine-loops and still frames must clearly display a single lead electrocardiographic recording in which P-, QRS-, and T-waves (but in particular the R wave) are clearly identifiable

### 7.3 Number of recorded heart cycles

- In sinus rhythm, record three continuous beats for all cine-loops and still frames, unless indicated otherwise.
- In the presence of irregular/non-sinus rhythm, record 5-10 continuous beats.
- Try to exclude premature beats.

### 7.4 Effects of respiration and timing of recordings

- During all recordings, respiration should be quiet.
- Tissue Doppler measurements should be recorded after non-forced end-expiration

### 7.5 Two-dimensional echocardiography general settings

- Use harmonic-imaging mode with maximized (mechanical index >1) power output
- Gain (and time-gain compensation (TGC)) settings should be adjusted to eliminate background noise and to allow for a clear blood-tissue border.
- An optimal gain setting consists of a left ventricular cavity with minimal (but not completely absent) noise
- The greyscale / dynamic range should be adjusted to provide an image with marked contrast between light and dark areas
- The focus point should be set at the middle of the region of interest
- Depth settings should be minimized (do not display structures outside the region of interest)

### 7.6 (Tissue) Doppler settings

- Use a display speed of 50 to 100 mm/sec and a sample volume length of 3-4 mm (in extremely low heart rates use a speed of 150 mm/sec).
- For mitral E-wave deceleration, time one recording is needed at a sweep speed of 150 mm/s
- Adjust gain, filter settings, position and velocity range to maximize the velocity excursion
- Minimize the angle between the direction of motion of the investigated structure or flow and the Doppler beam
- Transmitral flow should be assessed at the tips of the mitral valve
- Annotate the tissue Doppler recordings

### 7.7 Colour Doppler settings

- Minimize the colour sector and use a velocity range of approximately  $\pm 60$  cm/sec

### 7.8 Parasternal long-axis view

- Minimize the angle between the left ventricle and aorta (the inferolateral wall should be as perpendicular as possible to the transducer) the anteroseptal wall is visualized at the same distance from the transducer as the anterior wall of the ascending aorta

### 7.9 Apical two and four-chamber view

- The left ventricular apex should be visible in the top of the sector
- The aortic valve should be out of the image plane
- Maximize the internal long-axis of the left ventricle (avoid foreshortening) by looking for a window one intercostal space lower (in particular when the left ventricle does not appear ellipsoid)

- To ensure that the proper rotation has been made for a two-chamber view, the transducer is angled posteriorly to intersect both papillary muscles symmetrically. Then the transducer is angled slightly anteriorly so that neither papillary muscle is seen in its long axis in this view

#### 7.10 Special considerations for aortic regurgitation by colour flow imaging

In addition to the abovementioned recommendations:

- Standardize the machine settings for all examinations. Keep the Frame Rate around 20 Hz when recording colour Doppler aortic regurgitation
- Colour gain should be set step by step just below the appearance of colour noise artefacts
- For Vena contracta: use a parasternal long-axis view in ZOOM mode with minimal colour sector size and imaging depth to maximize lateral and temporal resolution
- For PISA: Shift the colour flow zero baseline downwards or upwards in the regurgitant jet direction in the left PLAX view depending on the jet orientation and upwards in the apical view)

#### 7.10 Subcostal window

In order to provide optimal image acquisition from subcostal window, the following steps are required:

- The knee-flexed position relaxes the upper abdominal muscles and thereby improves visualization
- From the subcostal four-chamber view, anti-clockwise rotation of the transducer permits visualization and pulsed Doppler examination of the upper abdominal aorta

[figure not shown]

## 8. Measurements of aortic root geometry

The following measurements of the aortic root are obtained from the parasternal long-axis view (screening/baseline exams only):

- **Aortic annulus long axis diameter.** The aortic annulus long axis diameter is measured perpendicular to the long axis of the root, measured between the endothelial point that trisects the posterior aortic wall, non-coronary cusp hinge and anterior mitral leaflet hinge (posterior hinge point), and the point that bisects the septal endocardium and the right coronary cusp hinge (anterior hinge point). Measurements should be made at mid-systole and inclusive of cusp calcifications (Figure 1). To accurately incorporate cusp calcification for aortic annulus sizing, measure from the white-black interfaces of the posterior and anterior aortic cusp hinge points and add 2 mm to the measurement.
- **Sinus of Valsalva diameter (SoV).** The SoV diameter is perpendicular to the long axis of the root and typically parallel to the aortic valve annulus. It is the widest intra-luminal distance within the sinuses (measured at end-diastole from inner edge to inner edge, Figure 2, A).
- **Sino-tubular junction diameter (STJ).** The STJ diameter is the intra-luminal diameter parallel to the SoV diameter, where the sinuses narrow and join the ascending aorta (measured at end-diastole from inner edge to inner edge, Figure 2, B).
- **Sinus of Valsalva height (SoVH).** The SoVH is the distance between the STJ and the aortic annulus long-annulus diameter (measured at end-diastole, Figure 3).

**Note:** *Measurements should be noted on images submitted for Screening Committee review*

**Figure 1.** Examples of measurement of the aortic annulus long axis diameter

[figure not shown]

Figure 2. Example of measurement of the Sinus of Valsalva (A) and Sino-Tubular Junction (B) diameters

[figure not shown]

[figure not shown]
Figure 3. Example of measurement of the Sinus of Valsalva Height (C)

### 9. Measurement of Left Ventricular Outflow Tract (LVOT) Diameter

[figure not shown]
The LVOT long axis diameter is measured in the parasternal long-axis view at early to mid systole. The optimal imaging plane is through the long axis of the aorta; therefore, the anterior and posterior walls of the aortic root should be parallel with the maximal aortic diameter.

For native aortic valves, the LVOT long axis diameter is measured from the white-black interface of the septal endocardium to the anterior mitral leaflet, parallel to the aortic valve plane and within 0.5 cm - 1 cm of the valve orifice (Figure 4). Following implantation of the CoreValve device, the LVOT diameters and the LVOT area are measured immediately proximal to the inflow aspect of the stent (Figure 5).

**Note: For optimal results, LVOT diameter is averaged from 3 measurements from 3 consecutive high quality 2D ZOOM views.**

**Figure 4.** TTE mid-systolic frame showing measurement of LVOT diameter for derivation of native aortic valve area.

[figure not shown]
**Figure 5.** Cursor placement for measurement of LVOT diameter for derivation of prosthetic effective orifice area

**10. Measurement of LVOT Velocity**

[figure not shown]
LVOT velocity is recorded with PW Doppler from the apical transducer position, either in the apical long-axis view or in the anteriorly angulated four-chamber view or “five-chamber view.” The PW sample volume is positioned just proximal to the aortic valve, with care to avoid the zone of pre-valve acceleration. The recommended procedure is to initially place the sample volume within the aortic valve leaflets (prosthetic or native), and then gradually move it apically until a clear spectral waveform is observed with a well-defined peak and minimal spectral broadening (Figure 6). No opening click should be seen. The optimal sample volume placement is usually between 0.5 and 1.0 cm upstream from the valve annulus. Post implantation, the sample volume should be placed at the entrance of the inlet of the TAV prosthesis.

**11. Measurement of Aortic Valve Velocity**

The aortic valve velocity and VTI should be interrogated with CW Doppler from all transducer positions (apical, right parasternal, suprasternal notch, left supraclavicular, subcostal). The position that provides the highest velocity is used for measurements. A smooth velocity curve with a clear outer edge and maximal velocity should be recorded. The maximal velocity is measured at the outer edge of the dark signal; fine linear signals at the peak should not be included in measurements. The outer edge of the dark “envelope” of the velocity curve is traced to provide both the VTI for the continuity equation and the mean gradient (Figure 7).

**Figure 6.** An optimal LVOT signal shows a smooth velocity curve with a narrow velocity range at each time point.

**Figure 7.** CW Doppler of severe AS jet showing measurement of maximal velocity and tracing of the Velocity curve to calculate mean gradient.

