#### C.6.10.1 Secondary Endpoints Tested to Support Labeling Claims

The following secondary endpoints will be tested, in order, to support labeling claims:

1. Transvalvular mean gradient at 12 months (non-inferiority): TAVI vs. SAVR (secondary objective #12). The hypothesis of interest is

$$H: \mu_{TAVI} < \mu_{SAVR} + 5$$

where  $\mu_{TAVI}$  and  $\mu_{SAVR}$  denote the average mean gradient from at 12 months, measured in mmHg. This objective will be evaluated using a Bayesian version of a two-sample t-test (see Section C.11). The posterior probability  $P(H | \text{data})$  will be calculated and compared to a threshold of 0.95.

2. Effective orifice area at 12 months (non-inferiority): TAVI vs. SAVR (secondary objective #12). The hypothesis of interest is

$$H: \mu_{TAVI} > \mu_{SAVR} - 0.1$$

where  $\mu_{TAVI}$  and  $\mu_{SAVR}$  denote the mean effective orifice area at 12 months, measured in  $\text{cm}^2$ . This objective will be evaluated using a Bayesian version of a two-sample t-test (see Section C.11). The posterior probability  $P(H | \text{data})$  will be calculated and compared to a threshold of 0.95.

3. Change in NYHA classification from baseline to 12 months (non-inferiority): TAVI vs. SAVR (secondary objective #8). The hypothesis of interest is

$$H: \mu_{TAVI} > \mu_{SAVR} - 0.375$$

where  $\mu_{TAVI}$  and  $\mu_{SAVR}$  denote the mean number of classification improvements in NYHA from baseline to 12 months. For subjects with NYHA categories at both baseline and 12 month visit, the NYHA classification improvements will be calculated as  $NYHA_{baseline} - NYHA_{12month}$ . This objective will be evaluated using a Bayesian version of a two-sample t-test (see Section C.11). The posterior probability  $P(H | data)$  will be calculated and compared to a threshold of 0.95.

4. Change in Kansas City Cardiomyopathy Questionnaire (KCCQ) score from baseline to 30 days (non-inferiority): TAVI vs. SAVR (secondary objective #11). The hypothesis of interest is

$$H: \mu_{TAVI} > \mu_{SAVR} - 5$$

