### 3. Four general rules for echocardiography recordings

3.1 Rule #1 for overall recordings: adhere STRICTLY to the PROTOCOL regarding:

- **number** and **order** of recordings as listed on the Table
- **do not perform measurements** on the echo recordings, except screening echo to be submitted for screening committee review (see measurements noted in section 4)
- at end of echo exam, export all required recordings in **DICOM** format and upload it to InteGRID
- only one **certified** echocardiographer (+ 1 replacement) is allowed to participate in the study, he/she should print his/her name, fill in contact details and sign the transmittal form

3.2 Rule #2 for Doppler recordings:

- Unless stated otherwise, all pulsed-wave and continuous-wave Doppler signals should be recorded at a **sweep speed of 50-100 mm/sec** (recording must contain minimum of three heartbeats) with optimized gain and filter setting, baseline position, and velocity range.

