### 4. Data requirements

Participating centers in the SURTAVI study should obtain the appropriate Doppler and echocardiography recordings to document the following variables.

- Aortic annulus long-axis diameter in mid-systole (screening/baseline only)\*
- LVOT long axis diameter in mid-systole
- Sinus of Valsalva diameter (SOV) at end diastole (screening/baseline only)\*
- Sino-tubular junction diameter (STJ) at end diastole (screening/baseline only)\*
- Sinus of Valsalva height (SOVH) at end-diastole (screening/baseline only)\*
- Max aortic valve velocity (V2) by CW Doppler
- Velocity time integral (VTI) across aortic valve by CW Doppler
- Mean gradient across aortic valve (MGV2) by CW Doppler\*
- Peak LVOT velocity (V1) by PW Doppler
- Velocity Ratio (V1 / V2)
- Velocity time integral (VTI) of LVOT velocity by PW Doppler
- Mean LVOT gradient (MGV1) by PW Doppler
- Doppler Velocity Index (DVI) =  $VTI_{LVOT} / VTI_{Ao}$
- Grade of aortic transvalvular regurgitation
- Grade of aortic paravalvular regurgitation
- Grade of mitral regurgitation
- PISA for MR (optional)
- Max tricuspid regurgitant (TR) jet velocity (if TR is present)
- Left ventricular (LV) end-diastolic diameter (LVEDD)
- Left ventricular (LV) end-systolic diameter (LVESD)
- Interventricular septal thickness at end diastole
- Left ventricular posterior wall thickness at end diastole
- Left atrial diameter (AP linear dimension) at end systole
- Left ventricular ejection fraction by visual estimate
- Heart rate from Doppler signal
- Mitral inflow "A" velocity
- Mitral inflow "E" velocity
- Mitral inflow E-wave deceleration time
- Mitral annular tissue Doppler systolic velocity (septal and lateral)
- Mitral annular tissue Doppler early diastolic velocity (septal and lateral)
- Mitral annular tissue Doppler late diastolic velocity (septal and lateral)

Procedures for acquiring aortic root measurements and key hemodynamic variables are described in the following sections. For Doppler velocities, the values reported should represent the average of measurements from at least three cardiac cycles for patients in sinus rhythm, and the average of measurements from five cardiac cycles for patients not in sinus rhythm. For aortic valve, TR jet, and tissue Doppler velocities, the reported values should represent the average of the highest velocities obtained from the same transducer position.

\* Screening/baseline measurements should be noted on the echo submitted for Screening Committee review.

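### The echo manual asks for aortic valve velocity from five transducer positions, but its mandatory recording list covers only two, so follow-up gradients may read low and valve areas high

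*Combined protocol and SAP*

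**What the plan says.** Three parts of Appendix R.7 bear on this.

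- **Section 11 (Measurement of Aortic Valve Velocity)** names five positions: "The aortic valve velocity and VTI should be interrogated with CW Doppler from all transducer positions (apical, right parasternal, suprasternal notch, left supraclavicular, subcostal"). It continues: "The position that provides the highest velocity is used for measurements". Section 4 (Data requirements) agrees that for aortic valve velocity "the reported values should represent the average of the highest velocities obtained from the same transducer position".
- **Section 3** opens with "Rule #1 for overall recordings: adhere STRICTLY to the PROTOCOL regarding" the number and order "of recordings as listed on the Table". The same rule tells sites not to measure on the recordings, except on the screening echo sent for Screening Committee review.
- **Table 1 (section 5)** lists CW aortic forward flow at item 37 (apical 5-chamber), item 49 (apical 3-chamber) and item 55, "CWD right parasternal aortic forward flow (frozen image"). The suprasternal and subcostal entries (items 53 and 54) are pulsed-wave recordings of diastolic aortic flow. There is no left supraclavicular entry. None of the optional items (57–60) is a CW trace from another position.

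In the main protocol, C.4.10 gives echo assessment to a core laboratory. C.6.10.1 begins the secondary label tests with "Transvalvular mean gradient at 12 months (non-inferiority"), margin 5 mmHg, followed by EOA at 12 months, margin 0.1 cm². Under C.6.10, testing stops at the first objective that misses its criterion. Secondary endpoints 5 and 6 in C.6.8.1 count a mean gradient of 20 mmHg or more as one marker of valve dysfunction.

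**The concern.** The highest-velocity rule works only if the best trace is stored. Table 1 is the list sites work from, and it is the list to which the strict instruction is tied. A site that finds its best signal at the suprasternal notch, left supraclavicular or subcostal position has no item under which to file it. At follow-up the site does not measure, and the core laboratory can choose only among the traces it receives.

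For any one recording the error runs one way: velocity and gradient too low, EOA and velocity ratio too high. Sites may also resolve the conflict differently, which would add variation between sites and visits. The quantities at stake are the 12-month gradient and EOA, which gate every later label claim, and the count of subjects at or above 20 mmHg.

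**Working it through.** The plan states no figure to reproduce. The check is a count, followed by an illustration with assumed inputs.

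**1. Count of positions**

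| Position named in section 11 | CW forward-flow item in Table 1 |
|---|---|
| Apical | 37 and 49 |
| Right parasternal | 55 |
| Suprasternal notch | none (53 is pulsed-wave, descending aorta) |
| Left supraclavicular | none |
| Subcostal | none (54 is pulsed-wave, abdominal aorta) |

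Five positions are required. Three items cover two of them, and three positions are uncovered.

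**2. Effect on one recording**

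Let the stored velocity fall short of the best available by a fraction f. The documents give no value, so f = 5%, 10% and 15% are assumed. Mean gradient is taken to scale with velocity squared, giving a factor (1−f)². EOA by the continuity equation has the aortic velocity integral in its denominator, giving a factor 1/(1−f).

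| | f = 5% | f = 10% | f = 15% |
|---|---|---|---|
| Gradient factor | 0.9025 | 0.81 | 0.7225 |
| EOA factor | 1.053 | 1.111 | 1.176 |
| 22 mmHg reads | 19.9 | 17.8 | 15.9 |
| True gradient below which the reading is under 20 mmHg: 20/(1−f)² | 22.2 | 24.7 | 27.7 |
| EOA of 1.8 cm² (assumed) reads | 1.89 | 2.00 | 2.12 |

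**3. Effect on the two label tests, same f in both arms**

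- Gradient: a true difference of 5 mmHg shrinks to 4.5, 4.1 or 3.6 mmHg. At f = 10% in every subject, a true TAVI excess of 5.5 mmHg would read 5.5 × 0.81 = 4.5, inside the margin.
- EOA: a true difference of 0.1 cm² stretches to 0.105, 0.111 or 0.118. At f = 10%, a true TAVI deficit above 0.1 × 0.9 = 0.09 cm² would already read beyond the margin.
- Dilution: if only a share p of subjects is affected, and this is unrelated to their gradient, the gradient difference is multiplied by 1 − p[1 − (1−f)²]. Bringing 5.5 down to 5 needs p = (1 − 5/5.5)/[1 − (1−f)²], where the numerator is 0.0909. At f = 10% that is 0.0909/0.19 = 48%. At 5% it is 0.0909/0.0975 = 93%, and at 15% it is 0.0909/0.2775 = 33%.
- Superiority tests of the same two measures compare with zero. A factor common to every subject scales the difference and its standard deviation alike, so those tests would not move.

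**4. Direction at screening**

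At f = 10%, a Vmax of 4.2 m/s reads 4.2 × 0.9 = 3.78, and a valve area of 0.95 cm² reads 0.95/0.9 = 1.06. Both move away from the severity criteria, so the error can exclude a patient but cannot admit one.

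**The case against.** The best reply is that section 11 already contains the answer. It tells sites to scan all positions and to record a clean curve with maximal velocity, and section 4 points to the later sections for how the key variables are acquired. Nothing forbids an extra clip, and the first-subject quality check in section 6.1 is against the protocol, not against Table 1 alone. A careful site could therefore store its best trace. A reader might infer that the highest-velocity rule cannot be applied at all. That goes too far. What stands is that Rule #1 ties strictness to the number of recordings on the Table, so two instructions in one manual pull apart and a compliant site may follow either.

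A reader might also infer widespread misclassification of eligibility. The documents do not support that:

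- Inclusion criterion 3 accepts catheter pressure recordings.
- C.4.1 allows a transthoracic echo up to 365 days old to confirm severe stenosis, and the repeat study it then requires need not re-measure valve area or gradient.
- Sites measure on the screening echo and so can see which window is best.
- Any remaining error excludes eligible patients before randomization.

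A third tempting reading is bias toward a TAVI success. Both arms use the same list, and a shared proportional under-read eases the gradient non-inferiority test while tightening the EOA one. No net direction follows.

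**Conclusion.** The inconsistency is certain: five positions in section 11 against two in the list sites are told to follow strictly. Its effect on results is possible but not quantifiable from the documents, which give neither the size of the under-read nor the share of subjects whose best window is unlisted. Under the assumed 5–15%, an affected recording reads gradient 10–28% low and EOA 5–18% high, and a true gradient in the low to middle twenties can fall under the 20 mmHg cut. Effects on arm means are diluted by the unknown share: at 10%, about half of all subjects would have to be affected before a true 5.5 mmHg excess slipped inside the 5 mmHg margin.

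Exposure is mainly at follow-up. Death or disabling stroke, the primary endpoint, does not depend on these recordings. The point is worth correcting because the remedy is cheap and a trace that was never stored cannot be recovered. It is not a threat to the main conclusion.

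**What to change.** Add one conditional item to Table 1, list H: CW aortic forward flow from whichever of the suprasternal notch, left supraclavicular and subcostal positions gives the highest velocity, if that exceeds items 37, 49 and 55, with the position annotated on the image. State in section 11 that the core laboratory measures the highest recorded trace.

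The cost is one manual revision and at most one extra clip per scheduled echo. R.7 section 2 lists eight (screening, discharge, 6, 12 and 24 months, and 3, 4 and 5 years), so at most eight clips per subject. Three compulsory clips at each echo, up to 24, are not needed, because only the best trace has to be kept. The annotation would also show how often an unlisted window is best, which is the figure now missing.
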